## Background and rationale

Although fluid administration is an almost universally used therapy in critical care, much is unknown about how to maximise benefits and minimise harms. There is a strong and consistent association between fluid accumulation in critical illness and poor outcomes, particularly mortality, in observational cohort studies of critically ill patients [1-4]. In a recent meta-analysis of 11 randomised trials (2051 patients), there was a non-significant reduction in mortality with a conservative or deresuscitative fluid strategy compared to a liberal strategy or usual care (RR 0.92, 95% CI 0.82 - 1.02). There was a significant reduction in ICU length of stay (mean difference (MD)-1.88 days, 95% CI -0.12, -3.64) and an increase in ventilator free days (MD 1.82 days, 95% CI 0.53, 3.10) with a conservative or deresuscitative strategy compared to a liberal strategy or standard care [5].

## Hypothesis

In critically ill patients, a post-resuscitation fluid strategy comprising conservative fluid administration and active deresuscitation reduces net fluid balance, is safe and improves outcomes.

## Objectives

1. To determine the feasibility, safety and clinical outcomes of conservative fluid administration and deresuscitation compared with usual care in critically ill patients
2. To explore biological effects of conservative fluid administration and deresuscitation.

## Study Methods

### Study Design

This will be a randomised, open-label, allocation concealed, pilot trial of conservative fluid administration and deresuscitation compared with usual care in adult patients who are critically ill. The intervention will consist of 2 stages: (1) conservative fluid administration and, if appropriate criteria are fulfilled, (2) deresuscitation in the form of diuretics or fluid removal using RRT to target a negative fluid balance.

### Randomisation

Patients will be randomised a minimum of 24 hours and a maximum of 48 hours following ICU admission. Randomisation will be stratified by study site. Subjects will be randomised in a 1:1 ratio using blocks of variable size.

### Sample Size Calculation

Based on data from a recent observational study in a similar population [2], we anticipate a fluid balance in the 24 hours up to day 3 (primary outcome) of  $494 \pm 1512$  mL in the usual care group. A sample size of 174 subjects (87 in each group) will have 90% power at a two-tailed significance level of 0.05 to detect a difference in fluid balance of 750 mL over 24 hours. We have allowed for a drop-out rate of 3% and the study will therefore require a total of 180 patients (90 in each group).

### Statistical analysis principles

The study will be analysed on an intention to treat basis. Multiple imputation will be used to deal with missing data. A p value of 0.05 will be considered as significant. A single final analysis is planned at the end of the trial.

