## Outcome measures and analysis

The primary endpoint is the fluid balance (mL) during the 24-hour period up to the beginning of study day 3 [continuous variable, measured using a Student's t-test for independent samples].

Secondary Outcomes		
Feasibility outcomes		
Cumulative fluid balance (mL) from ICU admission until the beginning of study days 3 and day 5, and at ICU discharge	Continuous variables	Independent samples t-test (or non-parametric equivalent)
Rates of recruitment as a proportion of patients screened and as a proportion of all patients admitted to ICU (per site)		Descriptive only
Incidence of significant protocol violations (total number of patients, per site, and by nature of protocol violation)		Descriptive only
Safety outcomes		
Incidence of serious adverse events (SAEs) (number of patients with SAEs as a proportion of total)		Chi-squared test / Fisher's exact test
Incidence of adverse events (AEs) (number of patients with AEs as a proportion of total)		Chi-squared test / Fisher's exact test
Efficacy outcomes		
Change in SOFA scores from baseline to the beginning of day 3 and beginning of day 5, overall and individual organ sub scores	Continuous variable	Multiple regression analysis (with baseline scores as covariate)
Mortality (28-day and 180 day)	Discrete variable	Chi-squared test; Kaplan-Meier survival curves; log-rank test +/- Cox proportional hazards model if assumptions met
Duration of mechanical ventilation in survivors and non-survivors	Continuous variable	Independent samples t-test (or non-parametric equivalent); Kaplan-Meier survival curves; log-rank test; +/- Cox proportional hazards model if assumptions met
Length of ICU stay	Continuous variable	Independent samples t-test (or non-parametric equivalent); Kaplan-Meier survival curves; log-rank test; +/- Cox

		proportional hazards model if assumptions met
Incidence of new acute kidney injury defined as KDIGO Stage 3 (before and after correction for fluid balance) up to the beginning of day 5	Discrete variable	Chi-squared test
Cognitive dysfunction at 180 days	Discrete variable	Chi-squared test
Health-related quality of life (HR-QoL) at 180 days	Ordinal variable	Mann-Whitney test
Incidence of anxiety and depression	Discrete variable	Chi-squared test
Incidence of Post-traumatic stress disorder	Discrete variable	Chi-squared test
Exploratory outcomes		

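### Multiple imputation is the rule for missing data, but the binary and ordinal endpoints get only chi-squared or Mann-Whitney tests, and no pooling method is named.

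*SAP*

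**What the plan says.** The SAP section Statistical analysis principles has one sentence on missing data: "Multiple imputation will be used to deal with missing data". It gives no scope, imputation model, number of imputations or pooling method. The same section says "The study will be analysed on an intention to treat basis" and "A p value of 0.05 will be considered as significant".

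The table under Outcome measures and analysis fixes a test for each endpoint:

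- New acute kidney injury, cognitive dysfunction, anxiety and depression, and post-traumatic stress disorder: chi-squared test.
- Adverse and serious adverse events: chi-squared or Fisher's exact test.
- "Health-related quality of life (HR-QoL) at 180 days": an ordinal variable, Mann-Whitney test.
- Mortality at 28 and 180 days: "Chi-squared test; Kaplan-Meier survival curves; log-rank test +/- Cox proportional hazards model if assumptions met".
- Change in SOFA score: regression on the baseline score. The primary endpoint, stated above the table, has a t-test.

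Under Secondary analyses there is a multiple regression with treatment as main exposure, but its outcomes are not named. Table 2 of the dummy tables has one P value for overall 28-day mortality. The only figure on attrition is the 3% drop-out in Sample Size Calculation.

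**The concern.** Multiple imputation yields several completed data sets. The usual way to reach one answer is to take an effect estimate and its variance from each and combine them by Rubin's rules. A chi-squared or Mann-Whitney test, as named, returns a statistic and a p value for each data set. The SAP fixes both the imputation and the tests but omits the step that joins them.

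Two things are at stake. First, the pooling method would be chosen after the data are in hand, for endpoints judged at 0.05. Second, tests alone give no effect size or confidence interval, which a pilot trial needs more than p values. The 180-day questionnaire outcomes are the most exposed, since follow-up to day 180 is likely to be less complete than data up to day 3.

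Mortality has a related gap. A fixed-time chi-squared test needs a yes or no for every patient, whereas Kaplan-Meier and log-rank can censor a patient whose status is unknown. The SAP gives no rule that covers both.

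**Working it through.** **1. The plan's own figure.** Inputs from Sample Size Calculation: difference 750 mL, SD 1512 mL, two-sided alpha 0.05, power 90%.

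n per arm = 2 × (1.960 + 1.282)² × (1512/750)² = 85.4, so 86. The t-test version gives 86.4, so 87, with power 0.902. Then 174/0.97 = 179.4, so 180. The stated 87 per group and 180 in total reproduce and are not in dispute. The drop-out allowance is 180 − 174 = 6 patients.

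**2. Rule against test.**

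| Endpoint | Named analysis | Estimate with standard error? |
|---|---|---|
| Primary fluid balance | t-test | Yes, mean difference |
| Change in SOFA | Regression | Yes, coefficient |
| New AKI, cognition, anxiety/depression, PTSD | Chi-squared | Not directly |
| AEs, SAEs | Chi-squared or Fisher | Not directly |
| HR-QoL | Mann-Whitney | Not directly |
| Mortality | Chi-squared; log-rank; conditional Cox | Only from the Cox model, if fitted |

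All seven binary rows and the one ordinal row name only a test, apart from the optional Cox model for mortality.

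**3. What pooling needs.** With m imputations, estimates Qj and variances Uj, Rubin's rules use Q̄ = mean of Qj, Ū = mean of Uj, B = variance of the Qj, and T = Ū + (1 + 1/m)B. Chi-squared statistics Wj can instead be combined by the D2 rule. For 1 df, r = (1 + 1/m) × var(√Wj) and D2 = [W̄ − r(m + 1)/(m − 1)]/(1 + r), referred to an F distribution. The SAP names neither.

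**4. Illustration, one data set.** Assumed: 90 per arm, event rates 35% v 20%, 50 imputations within arm.

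| Missing | Observed events | Range of single-data-set p | Rubin, risk difference | D2 |
|---|---|---|---|---|
| 3% | 30/87 v 17/87 | 0.008 to 0.065 | 0.022 | 0.024 |
| 10% | 28/81 v 16/81 | 0.004 to 0.18 | 0.033 | 0.035 |
| 20% | 25/72 v 14/72 | 0.002 to 0.31 | 0.030 | 0.032 |

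**5. Illustration, repeated trials.** Assumed: 60 assessed survivors per arm, true rates 30% v 45%, 20 imputations. The table gives the share of simulated trials whose 20 chi-squared p values fell on both sides of 0.05.

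| Missing | Share |
|---|---|
| 25% | about 62% |
| 10% | about 42% |
| 3% | 18% to 24%, varying between runs |

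At 25% missing, D2 and Rubin's rules on the risk difference reached the same decision at 0.05 in 98% to 99% of trials, with a median p difference of 0.007. The scenario sits near the threshold: 18/60 v 27/60 fully observed gives p = 0.09. With 30% v 60% and the same loss, the share falls to 38%.

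**6. Mortality.** Take a patient last known alive before day 28. The chi-squared test needs a status, so the general imputation rule would supply one. Kaplan-Meier would normally censor. The two results would agree on this patient only under a shared rule, such as imputing death times or censoring in both, and the SAP states none.

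**The case against.** The strongest reply is that nothing here is unworkable. A 2×2 table yields a risk difference or log odds ratio with a standard error, chi-squared statistics pool by D2, and Mann-Whitney and log-rank also have estimates or scores with variances. The spread of p values across imputed data sets is ordinary between-imputation variation, which pooling exists to absorb, and the SAP nowhere proposes to report a single data set. All of this stands. A reader might infer that the named tests cannot be combined at all; that reading is wrong. What remains is that the SAP picks none of these routes and plans no effect with a confidence interval for these endpoints.

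A reader might also infer that the SAP itself imputes lost patients in one mortality test and censors them in the other. The text does not say so. It speaks only of missing data, mentions neither withdrawal nor censoring, and the protocol, which is not at hand, may cover withdrawn patients. The double treatment is a likely consequence of a missing rule, not a stated contradiction.

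The dummy tables are described as indicative of presentation only, and the counts in the 28-day mortality row sit naturally with the chi-squared test. That weakens the Table 2 point to a request for clarity. The affected endpoints are secondary, in a pilot trial, with 180-day results reserved for a separate manuscript.

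The secondary regression would give poolable estimates, but it names no outcomes and so does not close the gap.

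**Conclusion.** The point holds in a limited form. The SAP prescribes multiple imputation, assigns the binary and ordinal endpoints tests that do not directly give what Rubin's rules combine, and names no pooling method. The change should be made, but the point does not threaten the primary result: the t-test and the SOFA regression pool as they stand.

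The size depends on how much is missing. At 3% the pooled answer barely depends on the method (0.022 against 0.024 in the illustration), though even there a single data set can land on either side of 0.05. With heavier loss the spread widens, and the consequence of leaving the method open grows. The 25% loss, the event rates and the number of assessed survivors are assumptions; the SAP gives no rate of loss at day 180. The simulated 62% shows why a pooling rule must be fixed in advance. It is not an error rate of the plan.

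**What to change.** Amend the SAP as follows:

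- State which endpoints are imputed, the imputation model and the number of imputations.
- For each imputed binary endpoint, replace the chi-squared test with a logistic model (or a risk difference) with arm and site. Site is the randomisation stratum.
- For HR-QoL, replace Mann-Whitney with a proportional-odds model with arm and site.
- Pool by Rubin's rules and report the effect, 95% CI and p value.
- For mortality, apply one rule for unknown vital status to both analyses. One example: do not impute, censor at last contact, and take the 28- and 180-day risk differences from the Kaplan-Meier estimates. This keeps every randomised patient in both results; using known status only for the risk difference would drop lost patients from one result and censor them in the other.
- State which mortality result fills the P value in Table 2.

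The cost is SAP wording. The sample size and data collection do not change. The small downside is the proportional-odds assumption, which Mann-Whitney does not state. The mortality example also assumes that censoring is unrelated to prognosis, as the planned log-rank test already does.

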## Subgroup analyses

We will compare the primary outcomes and clinical outcomes between treatment groups in the following subgroups: patients with and without Acute Respiratory Distress Syndrome, Sepsis, Traumatic Brain Injury, and with hyper- and hypo-inflammatory phenotypes as previously defined [6].

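### The SAP's 0.05 significance rule is not confined to the primary outcome, so chance results among roughly 70 unadjusted secondary and exploratory comparisons may be called significant

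*SAP*

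**What the plan says.** The Sample Size Calculation section bases the trial on the primary outcome alone: "A sample size of 174 subjects (87 in each group) will have 90% power". The target there is a between-group difference of 750 mL, tested two-sided at the 5% level. Statistical analysis principles then gives one general rule, "A p value of 0.05 will be considered as significant", and names no class of outcome to which it applies. The same section plans one final analysis, so repeated looks over time are not at issue.

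The table under Outcome measures and analysis attaches a test to almost every secondary and exploratory row. One row alone covers "Change in SOFA scores from baseline to the beginning of day 3 and beginning of day 5, overall and individual organ sub scores". Only two rows, recruitment rates and protocol violations, are marked as descriptive.

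Under Subgroup analyses the SAP adds: "We will compare the primary outcomes and clinical outcomes between treatment groups in the following subgroups". Secondary analyses adds a covariate-adjusted regression, a per-protocol analysis, and a path analysis that depends on there being evidence of a group difference in cognitive dysfunction.

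The dummy tables, described as indicative, show P-value cells for non-primary rows of Table 2 and for the adverse-event rows of Table 3. The note after Table 3 sends the 180-day and exploratory outcomes to a separate paper.

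**The concern.** An unadjusted 0.05 threshold is sound for one pre-specified primary test. Once the same verdict is available to dozens of other tests, some will meet it by chance, and the SAP gives the reader no way to tell such a result from a controlled one. It contains no testing hierarchy, no multiplicity procedure and no sentence on how secondary or exploratory p values should be read.

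The stated hypothesis is that the strategy "reduces net fluid balance, is safe and improves outcomes". The last part names no particular outcome, so a nominally low p value on any clinical outcome could be put forward as significant support.

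The rule may also steer the analysis itself. The only yardstick the SAP offers for evidence of a difference in cognitive dysfunction is the 0.05 rule, so an uncontrolled secondary result could decide whether a mediation analysis is run.

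**Working it through.** **1. The plan's own figure.** Inputs from Sample Size Calculation: difference 750 mL, SD 1512 mL, two-sided alpha 0.05, power 90%. Allocation is 1:1 (Randomisation).

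- Normal approximation: n per group = 2 × (1.960 + 1.2816)² × (1512/750)² = 2 × 10.507 × 4.064 = 85.4, so 86.
- Noncentral t: 86 per group gives power 0.899 and 87 gives 0.902, so 87 per group, 174 in total.
- Dropout: 174 / 0.97 = 179.4, so 180.

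The stated 174 and 180 are reproduced, for one test at two-sided 0.05.

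**2. Counting the other comparisons.** Two assumptions are needed, because the SAP does not give the figures: six SOFA organ sub-scores, and one time point per biomarker.

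| Secondary | Tests |
|---|---|
| Cumulative fluid balance (day 3, day 5, ICU discharge) | 3 |
| SAEs, AEs | 2 |
| SOFA: (total + 6) × 2 times | 14 |
| Mortality (28 and 180 days) | 2 |
| Ventilation (survivors, non-survivors) | 2 |
| ICU stay | 1 |
| New AKI (before and after correction) | 2 |
| Cognition, quality of life, PTSD | 3 |
| Anxiety, depression | 2 (1 if combined) |
| **Total** | **31 (30)** |

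| Exploratory | Tests |
|---|---|
| Endothelial: 7 markers × (level, change) | 14 |
| Inflammatory: 4 named × (level, change) | 8 |
| Echocardiography: 2 named | 2 |
| Renal: 2 markers × 2 fluids × (level, change) | 8 |
| Cerebral oximetry: mean, minimum, 3 thresholds | 5 |
| Muscle oxygenation: mean, minimum | 2 |
| **Total** | **39** |

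Together these make 70, or 69 if anxiety and depression are one outcome. The log-rank tests named for mortality, ventilation and ICU stay add 4 or 5. The range is therefore 69 to 75.

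**3. Expected results below 0.05 with no true effect.** This is k × 0.05 and does not depend on correlation: 70 × 0.05 = 3.5; 74 × 0.05 = 3.7; the 31 secondary comparisons alone, 1.55.

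**4. Chance of at least one.** If independent, this is 1 − 0.95^k: 97.2% for k = 70, 97.8% for k = 74, and 79.6% for k = 31.

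Correlation lowers it. The SAP gives no correlations, so these are assumed values, with simulated normal test statistics and k = 74:

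| Assumed correlation | At least one below 0.05 |
|---|---|
| Common 0.2 | 94% |
| Common 0.3 | 89% |
| Common 0.5 | 71% |
| Common 0.7 | 46% |
| 0.7 to 0.9 within a table row, 0 to 0.3 between rows | 69% to 89% |

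**5. The main report.** Table 2 has eight non-primary P-value cells: cumulative balance to days 3 and 5, total 28-day mortality, ventilation, ICU stay, SOFA change to days 3 and 5, and new AKI. If independent, 1 − 0.95^8 = 34%, with 8 × 0.05 = 0.4 expected. Table 3 adds P-value cells for adverse events, including the three most frequent individually.

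**The case against.** The strongest reply is that the trial is a pilot with one named primary endpoint, that everything else is labelled secondary or exploratory, and that unadjusted secondary analysis is normal in that setting. The last part stands: neither a multiplicity correction nor a larger trial is needed. But no sentence ties those labels to how a result may be described, and the 0.05 rule has no such limit. Where the authors wanted a row to be descriptive they said so, for two rows only.

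Several points on size also stand:

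- The count of 69 to 75 includes overlapping tests: log-rank tests on outcomes already tested another way, level and change for the same marker, and AKI before and after correction.
- Cumulative balance to day 3 contains the primary outcome's 24 hours, so a null there is implausible if the intervention works. The no-effect calculation is a benchmark and does not forecast the trial's results.
- On the other side, the mediator and echocardiography lists are open-ended, and subgroup, regression and per-protocol analyses are not counted. The count is therefore not an upper bound.

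Three stronger readings are tempting and are not supported:

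- *The main paper will almost certainly contain a false positive.* The 98% pools outcomes that the SAP sends to a separate paper, and SOFA sub-scores that it sends to an appendix. Table 2 also leaves its four mortality subgroup rows without a P value.
- *Every chance result would count as evidence of benefit.* With two-sided tests about half would favour usual care, and biomarker or adverse-event results do not show improved outcomes. With 25 efficacy comparisons (14 SOFA, 2 mortality, 2 ventilation, 1 ICU stay, 2 AKI, 4 long-term), 25 × 0.025 = 0.63 favourable chance results are expected, and 1 − 0.975^25 = 47% is the chance of at least one if independent.
- *Chance findings would shape a definitive trial.* The SAP does not mention one.

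**Conclusion.** The point holds as a defect in the significance rule. As written, the SAP permits any secondary, exploratory or subgroup result at p = 0.05 to be called significant, although only the primary comparison was planned to support that word. At least one chance result somewhere in the full set is likely under most plausible correlations. It becomes less likely than not only when a very high common correlation, about 0.7 or more, runs across all outcomes. These figures rest on no true effect on any outcome, six SOFA sub-scores and one time point per biomarker.

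The main report's exposure is smaller but not negligible. A reader might infer that the trial's principal conclusion is compromised. It is not: there is one primary endpoint, one final analysis, and a sample size that reproduces. What is at risk is the wording of secondary claims and the trigger for the path analysis.

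**What to change.** Replace the general significance sentence in Statistical analysis principles with:

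> *The two-sided 5% significance level applies to the primary outcome only. All secondary, exploratory, subgroup, adjusted and per-protocol results are reported as effect estimates with 95% confidence intervals, unadjusted for multiplicity; any p values are nominal and are not described as statistically significant.*

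Two further edits are needed for consistency:

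- In dummy Tables 2 and 3, mark the non-primary P values as nominal or drop them.
- In Secondary analyses, make the path analysis of cognitive dysfunction exploratory and do not let a significance verdict on that outcome trigger it. Otherwise, confining the 5% level to the primary outcome leaves that step with no stated criterion.

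The cost is one replaced sentence, the table labels and one reworded condition. Data collection, sample size and the primary analysis do not change. The real downside is that no secondary result can be headlined as significant.

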## Outcome measures and analysis

The primary endpoint is the fluid balance (mL) during the 24-hour period up to the beginning of study day 3 [continuous variable, measured using a Student's t-test for independent samples].

Secondary Outcomes		
Feasibility outcomes		
Cumulative fluid balance (mL) from ICU admission until the beginning of study days 3 and day 5, and at ICU discharge	Continuous variables	Independent samples t-test (or non-parametric equivalent)
Rates of recruitment as a proportion of patients screened and as a proportion of all patients admitted to ICU (per site)		Descriptive only
Incidence of significant protocol violations (total number of patients, per site, and by nature of protocol violation)		Descriptive only
Safety outcomes		
Incidence of serious adverse events (SAEs) (number of patients with SAEs as a proportion of total)		Chi-squared test / Fisher's exact test
Incidence of adverse events (AEs) (number of patients with AEs as a proportion of total)		Chi-squared test / Fisher's exact test
Efficacy outcomes		
Change in SOFA scores from baseline to the beginning of day 3 and beginning of day 5, overall and individual organ sub scores	Continuous variable	Multiple regression analysis (with baseline scores as covariate)
Mortality (28-day and 180 day)	Discrete variable	Chi-squared test; Kaplan-Meier survival curves; log-rank test +/- Cox proportional hazards model if assumptions met
Duration of mechanical ventilation in survivors and non-survivors	Continuous variable	Independent samples t-test (or non-parametric equivalent); Kaplan-Meier survival curves; log-rank test; +/- Cox proportional hazards model if assumptions met
Length of ICU stay	Continuous variable	Independent samples t-test (or non-parametric equivalent); Kaplan-Meier survival curves; log-rank test; +/- Cox

		proportional hazards model if assumptions met
Incidence of new acute kidney injury defined as KDIGO Stage 3 (before and after correction for fluid balance) up to the beginning of day 5	Discrete variable	Chi-squared test
Cognitive dysfunction at 180 days	Discrete variable	Chi-squared test
Health-related quality of life (HR-QoL) at 180 days	Ordinal variable	Mann-Whitney test
Incidence of anxiety and depression	Discrete variable	Chi-squared test
Incidence of Post-traumatic stress disorder	Discrete variable	Chi-squared test
Exploratory outcomes		
Plasma levels of markers of endothelial injury (Angiopoietin I/II and Ang-1/2, Syndecan-1, total protein, plasma albumin, and protein permeability (albumin: $\alpha$ 2-macroglobulin ratio)), absolute levels and change from baseline	Continuous variables	Independent samples t-test (or non-parametric equivalent); Repeated measures ANOVA if applicable. Scatterplots and Pearson's correlation coefficient or non-parametric alternative if applicable.
Plasma levels of Inflammatory mediators e.g. CRP, TNF $\alpha$ , IL6, IL8: absolute levels and change from baseline	Continuous variables	Independent samples t-test (or non-parametric equivalent); Repeated measures ANOVA if applicable. Scatterplots and Pearson's correlation coefficient or non-parametric alternative if applicable.
Cardiac function (echocardiographic measures including left ventricular ejection fraction, E/E' ratio)	Continuous variables	Independent samples t-test (or non-parametric equivalent)
Renal function and injury (plasma and urine levels of Cystatin C and NGAL), absolute levels and change from baseline	Continuous variables	Independent samples t-test (or non-parametric equivalent); Repeated measures ANOVA if applicable. Scatterplots and Pearson's correlation coefficient or non-parametric alternative if applicable.
Cerebral oximetry (NIRS measurement of regional cerebral oxygen saturation), mean and minimum rScO 2 level, proportion of time spent with rScO 2 below thresholds of 50%, 65%, and 75%	Continuous variables	Independent samples t-test (or non-parametric equivalent)
Tissue oxygenation (NIRS measurement of muscle tissue oxygen saturation), mean and minimum rScO 2 level	Continuous variables	Independent samples t-test (or non-parametric equivalent)

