## Secondary analyses

Secondary multiple regression analysis will be performed with treatment allocation as the main exposure. The following key covariates will be forced into the model: age, APACHE II score, presence of ARDS, vasopressor use at baseline. Additional covariates for inclusion in the model will be selected based on clinical plausibility.

We will undertake a secondary per-protocol analysis. This information will be valuable in differentiation between treatment failure (the treatment did not have the intended effect) and process failure (intervention not delivered as intended).

If there is evidence of a difference in the outcome of cognitive dysfunction between treatment groups, we will use path analysis to attempt to ascertain whether the effect of treatment group assignment on cognitive function is mediated by cerebral oxygenation.

For the exploratory outcomes, we will undertake secondary analyses using multivariate regression analysis with fluid balance as the main exposure and treatment group assignment as a covariate.

At a later stage, we will investigate the relationship between cerebral and tissue oxygenation and cardio-respiratory physiological variables such as heart rate, mean arterial pressure, and arterial oxygen saturation.

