## Dummy Tables and Diagrams

The following are indicative of the approach used to present data, rather than the precise format.

Figure 1. Study flow diagram.

[figure not shown]

Table 1. Patient characteristics at randomisation.

Variables	Control	Intervention
Age	Mean (SD)	Mean (SD)
Gender:		
Male	N (%)	N (%)
Female	N (%)	N (%)
Type of admission:		
Emergency	N (%)	N (%)
Elective	N (%)	N (%)
Operative status:		
Surgical	N (%)	N (%)
Non-surgical	N (%)	N (%)
Primary organ system involvement:		
Respiratory	N (%)	N (%)
Cardiovascular	N (%)	N (%)
Neurological	N (%)	N (%)
Renal	N (%)	N (%)
Gastrointestinal	N (%)	N (%)
Other	N (%)	N (%)
Subgroups:		
Acute Respiratory Distress Syndrome	N (%)	N (%)
Sepsis	N (%)	N (%)
Traumatic Brain Injury	N (%)	N (%)
Hyperinflammatory phenotype	N (%)	N (%)
APACHE II score	Mean (SD)	Mean (SD)
Baseline SOFA score	Mean (SD)	Mean (SD)
KDIGO stage:		
1	N (%)	N (%)
2	N (%)	N (%)
3	N (%)	N (%)
Vasopressor use	N (%)	N (%)
Serum lactate	Mean (SD)	Mean (SD)
Renal Replacement Therapy use	N (%)	N (%)
Oxygenation index	Mean (SD)	Mean (SD)
Oedema in > 1 peripheral site	N (%)	N (%)
Cumulative fluid balance	Mean (SD)	Mean (SD)

Table 2. Key outcomes

	Control	Intervention	P value
Primary outcome			
Fluid balance over 24 hours up to Day 3 (mL)	Mean (SD)	Mean (SD)	x.xxx
Feasibility outcomes			
Cumulative fluid balance from ICU admission up to Day 3	Mean (SD)	Mean (SD)	x.xxx
Cumulative fluid balance from ICU admission up to Day 5	Mean (SD)	Mean (SD)	x.xxx
Clinical outcomes			
Mortality at 28 days:			
Total	N (%)	N (%)	x.xxx
Acute Respiratory Distress Syndrome	N (%)	N (%)	
Sepsis	N (%)	N (%)	
Traumatic Brain Injury	N (%)	N (%)	
Hyperinflammatory phenotype	N (%)	N (%)	
Duration of mechanical ventilation in survivors	Median (IQR) # , N=x	Median (IQR) # , N=x	x.xxx
Length of ICU stay in survivors	Median (IQR) # , N=x	Median (IQR) # , N=x	x.xxx
Change in SOFA scores baseline to day 3	Mean (SD)	Mean (SD)	x.xxx
Change in SOFA scores baseline to day 5	Mean (SD)	Mean (SD)	x.xxx
Incidence of new AKI (KDIGO Stage 3)	N (%)	N (%)	x.xxx
Before correction for fluid balance			
After correction for fluid balance			

\*Individual SOFA organ function scores to be reported in an appendix. #Mean (SD) to be reported if normally distributed

Table 3. Process measures

Recruitment rates (% of screened patients / % of admitted patients)*:			
Total	xx.x% / yy.y%		N/A

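### The primary analysis is an unadjusted t-test that ignores site, the stratification factor, and fluid balance at randomisation; it is valid but may give up precision at little cost

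*SAP*

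**What the plan says.** - **Endpoint and test** (SAP, Outcome measures and analysis): "The primary endpoint is the fluid balance (mL) during the 24-hour period up to the beginning of study day 3". The method is given as "continuous variable, measured using a Student's t-test for independent samples", with no covariate and no site term.
- **Allocation** (SAP, Randomisation): "Randomisation will be stratified by study site", 1:1, in blocks of varying size.
- **Sample size** (SAP, Sample Size Calculation): 87 per group for "90% power at a two-tailed significance level of 0.05 to detect a difference in fluid balance of 750 mL", with an SD of 1512 mL.
- **Baseline data** (SAP, Dummy Tables and Diagrams, Table 1): "Cumulative fluid balance" is among the characteristics tabulated at randomisation.
- **Secondary regression** (SAP, Secondary analyses): "The following key covariates will be forced into the model: age, APACHE II score, presence of ARDS, vasopressor use at baseline". Neither site nor baseline fluid balance is on that list. A further sentence leaves the door open: "Additional covariates for inclusion in the model will be selected based on clinical plausibility".
- **Another outcome** (SAP, Outcome measures and analysis, SOFA row): change in SOFA is analysed by "Multiple regression analysis (with baseline scores as covariate").

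**The concern.** There are two separate points, with different consequences.

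**Site.** Blocked randomisation within site balances the arms on site, which removes between-site variation from the treatment contrast. The pooled SD of the t-test still contains that variation. If site predicts fluid balance, the standard error is too large for the design used, p-values are somewhat too large, and the actual type I error falls below the nominal 5%. If site predicts nothing, there is no effect.

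**Baseline fluid balance.** Leaving it out does not affect type I error. It only forgoes precision, and only if the baseline value predicts the 24-hour balance.

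What is at stake is the width of the confidence interval for the pilot's main estimate. The open covariate clause under Secondary analyses does not settle the matter: it would allow both variables, but it commits to neither in advance and concerns a secondary model only. Choosing them after the data are seen could look data-driven.

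**Working it through.** **Inputs from the SAP:** difference 750 mL, SD 1512 mL, two-sided alpha 0.05, 87 per arm (174 evaluable), 3% drop-out. **Assumptions (not in the SAP):** v, the share of outcome variance explained by site; r, the correlation of baseline with outcome; R², the share explained by site and baseline together; and the number of sites.

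**1. The plan's own figure.** SE = 1512 × √(2/87) = 229.2 mL. With 172 df the critical value is 1.974, so the 95% CI half-width is 1.974 × 229.2 = 453 mL. The noncentrality is 750/229.2 = 3.27, and noncentral-t power is 90.2%. At 86 per arm power is 89.9%, so 87 is the smallest number that reaches 90%. Drop-out: 174/0.97 = 179.4, rounded up to 180. The plan's 174 and 180 are reproduced.

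**2. Site ignored.** If blocking balances site fully, the true SE is 229.2 × √(1−v) while the t-test still uses about 229.2. Type I error = 2 × P(T₁₇₂ > 1.974/√(1−v)). Power uses SD 1512 × √(1−v) with the same raised critical value.

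| v (assumed) | Type I error | Power of unadjusted t-test |
|---|---|---|
| 0 | 5.0% | 90.2% |
| 0.05 | 4.4% | 90.8% |
| 0.10 | 3.9% | 91.3% |

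Simulation agrees (40,000 trials per setting, 174 patients, 3, 5 or 10 equal sites, blocks of 4 assumed). Unadjusted type I error was 4.5% at v = 0.05 and 3.9% to 4.0% at v = 0.10. The adjusted test stayed between 4.8% and 5.2% throughout.

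**3. Site and baseline adjusted.** Residual SD = 1512 × √(1−R²), put into the formulas of step 1.

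| R² (assumed) | Residual SD | 95% CI half-width | Power at 750 mL | Difference detectable at 90% power |
|---|---|---|---|---|
| 0 | 1512 mL | 453 mL | 90.2% | 747 mL |
| 0.10 | 1434 mL | 429 mL | 92.9% | 709 mL |
| 0.20 | 1352 mL | 405 mL | 95.3% | 668 mL |

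The power gain is not always the difference from 90.2%, because the unadjusted test already has slightly higher power when site is prognostic. With R² = 0.10 and 5 sites, simulated power rises from 91.3% to 92.8% if all of it comes from site (1.5 points), and from 90.1% to 92.6% if all of it comes from baseline (2.5 points; 2.7 by formula, 90.2% to 92.9%).

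**4. Weak baseline correlation.** With one covariate, R² = r² and df = 171. Power is 90.5% at r = 0.1, 91.3% at r = 0.2, 92.7% at r = 0.3 and 96.4% at r = 0.5. The matching evaluable sample size, 174 × (1−r²), is about 172, 167, 158 and 131. An R² of 0.10 from baseline alone needs r = √0.10 = 0.32; 0.20 needs r = 0.45.

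**5. Cost if neither variable predicts.** With equal sites, simulated power goes from 90.3% to 90.0% at both 5 and 10 sites. With unequal sites and variable blocks, the worst-case loss was about 0.3 to 0.5 points at 5 to 10 sites and about 1 point at 20.

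**The case against.** The strongest reply is that this is a preference and not an error. The trial is sized for a comparison of two means and analysed with the matching test. The method is fixed in advance and unambiguous, and its planned power is met. All of that stands.

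Three further points carry weight:

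- **Uncertain gain.** The baseline variable is cumulative balance since ICU admission, not an earlier 24-hour balance. Patients are randomised 24 to 48 hours after admission, so the period it covers can differ twofold. Its correlation with the endpoint may be modest, and at r = 0.2 or below the gain is about one power point.
- **SOFA is a weak precedent.** There the covariate is the same score measured earlier. The SAP is therefore not inconsistent in treating the two outcomes differently; the SOFA row shows only that baseline adjustment is already part of its methods.
- **Cost depends on the sites.** Many small sites or incomplete blocks make site terms dearer and within-site balance looser. The less favourable simulation puts the loss at about 1 point with 20 sites, which is still small.

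The planned adjusted regression answers the point only in part. It is secondary, and it names neither the factor used to randomise nor the listed baseline measure closest in kind to the outcome. These objections limit how much the point matters; they do not remove it.

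**Conclusion.** The concern holds, as a point of efficiency. The unadjusted t-test is unbiased, does not inflate type I error and meets the stated power, so nothing here invalidates the plan. It is mildly conservative to the extent that site predicts fluid balance: about 4.4% or 3.9% actual type I error at assumed site shares of 5% or 10%. It also gives a wider interval than the same data could support if site or baseline is predictive: 453 mL against 429 or 405 mL at an assumed combined R² of 0.10 or 0.20. The realistic power gain runs from nil to a few points. Its size cannot be fixed from the SAP, which gives neither the number of sites, the site variance share nor the baseline correlation. The change is recommended because it uses data already planned and costs little even if neither variable proves predictive.

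**What to change.** 1. Make the primary analysis a linear regression of 24-hour fluid balance on treatment, site and cumulative fluid balance at randomisation. Report the adjusted mean difference with its 95% CI and p-value.
2. Write the rule for pooling small sites into the SAP before the data are seen. At the least, it should cover any site without patients in both arms.
3. Keep the unadjusted t-test as a sensitivity analysis.
4. Add site and cumulative fluid balance at randomisation to the forced covariates of the secondary regression, so that neither depends on a later judgement of plausibility.

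The cost is SAP wording: no new data, no more patients, and the sample size stays at 180. If neither variable predicts the outcome, the site terms cost about 0.3 to 0.5 power points with 5 to 10 sites and about 1 point with 20.
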